#### 3. Study design

This was a randomized, double-blind study without placebo. Forty patients with physician-diagnosed IBS-D were recruited. The recruited patients were randomly assigned to undergo either real tVNS (transcutaneous vagus nerve stimulation) or sham TVNS (using the same device but without vagus nerve stimulation) at different times.

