#### **6.Study PROCEDURE**

Stool samples were collected from patients with diarrhea-type irritable bowel syndrome. The auricular concha-stimulator was used for 3 hours per day with a pulse width of 200µs and a frequency of 30Hz. Each patient was randomly selected for true stimulation or sham stimulation every 4 weeks for 8 weeks, resulting in a total of 4 groups, namely, true-true, true-false, false-true, and false-false (FIG. 2). Stool samples were collected on day 0, day 28 and day 56. Stool samples were collected two weeks after the end of the treatment. Patients completed questionnaires on day 0 and every other 7 days thereafter, for a total of 11 questionnaire collections (Figure 1); the questionnaires are shown in Table 2.

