#### Figure 2 Schematic representation of patient randomization

A questionnaire was used to determine whether the symptoms of patients with irritable bowel syndrome improved, and stool samples were collected on days 0, 28, 56, 63, and 70 for 16s sequencing analysis. To study the changes in intestinal microbial composition and intestinal marker metabolites in patients before and after the intervention of ear conchal stimulator. Continuous sampling survey was conducted 2 weeks after treatment to observe the long-term effect of tVNS treatment, and to explore whether the irritable bowel level of patients would return to the level before treatment or could be improved after stopping the stimulation.

The study did not require recruitment advertisement, and the recruitment of subjects was completely voluntary. The possible risks in the process of the study were explained to the subjects, and the subjects signed the informed consent form after they agreed to participate in the study. A questionnaire survey was conducted on the volunteers who agreed to participate in the study to obtain their intestinal health and other health status. The subjects were screened according to the above selection criteria and exclusion criteria. The collected samples were named by number, and no personal information of the subjects was disclosed. The identity of the subjects was kept confidential throughout the study, only the number and disease phenotype were visible. Subjects may withdraw from the study at any time stage.

The composition and structure of gut microbiota of the subjects will be analyzed. Subjects can keep informed of the progress of the experiment and analysis and obtain their own relevant data at any time.

The auricular conchal stimulator used in this study was manufactured by Ruisenan Medical Company. The portable conchal stimulator used in this study was in the form of earphones, which was well accepted by patients. It is easy to use and can be used at night before going to bed without affecting the normal life of the participants. The contact point of the earphone was closely fitted to the left ear conchial boat, which precisely stimulated the conchial boat and gave full play to the therapeutic effect. The instrument has three optional modes to meet the needs of personalized treatment.

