#### 9. Data collection and statistical analysis

The degree of pain, the frequency of diarrhea, and the degree of abdominal distension were used to evaluate the changes in the patient's irritable bowel status. The degree of pain refers to the use of psychometric practices to evaluate the patient's subjective feeling, which is also considered to be the main factor to evaluate the poor health-related quality of life (HRQL). The severity of irritable bowel syndrome was measured according to the Gastrointestinal Symptom Rating Scale for Irritable Bowel Syndrome (GSRS-IBS). On the GSRS-IBS scale, a score of 1 to 3 is defined as mild symptoms, a score of 4 or 5 as more severe, and a score of 6 or 7 as extremely severe.

Two-way analysis of variance (ANOVA) was used for statistical analysis. Two-sided t test was used for pairwise comparison, and p value was corrected for multiple comparisons. Kruskal-Wallis test was used for multiple group comparison. Spearman correlation analysis was used to determine the correlation between gut microbiota alterations and biological and pathological parameters related to constipation, with p values corrected by Benjamini-Hochberg method (Benjamini and Hochberg, 1995). A False Discovery Rate (FDR) threshold of 0.1 was used to consider the p value statistically significant. p < 0.05 or p < 0.01 was considered statistically significant. All rule plots were generated using GraphPad Prism version 8.0 (La Jolla, CA, United States). All statistical analyses were performed using GraphPad prismore and R(version 4.1.2,https://www.r-project.org/)

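### Participants may follow the analysis and obtain their own data at any time, with no limit that protects the blind while they are still rating their symptoms

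*Combined protocol and SAP*

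**What the plan says.** Section 3 (Study design) states: "This was a randomized, double-blind study without placebo". The comparator is described there as "sham TVNS (using the same device but without vagus nerve stimulation".

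Section 6 (Study PROCEDURE) sets the allocation: "Each patient was randomly selected for true stimulation or sham stimulation every 4 weeks", which over 8 weeks gives four sequences. It also sets the questionnaire schedule: "Patients completed questionnaires on day 0 and every other 7 days thereafter, for a total of 11 questionnaire collections".

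Under the Figure 2 heading, the protocol says how benefit is judged: "A questionnaire was used to determine whether the symptoms of patients with irritable bowel syndrome improved". It adds that "stool samples were collected on days 0, 28, 56, 63, and 70 for 16s sequencing analysis". Section 9 (Data collection and statistical analysis) uses pain, diarrhoea frequency and distension, with severity on the GSRS-IBS. It describes the pain rating as a way to "evaluate the patient's subjective feeling".

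The rule at issue is also under the Figure 2 heading, directly after a sentence saying that participants' gut microbiota will be analysed: "Subjects can keep informed of the progress of the experiment and analysis and obtain their own relevant data at any time".

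The nearest protection in that text is confidentiality of identity. It governs what others can see about a participant, not what the participant may be told.

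**The concern.** A sham comparison of self-rated symptoms depends on participants not knowing, or coming to believe they know, which stimulation they are receiving. The access rule is a positive statement, not a missing detail, and it is open in two respects. It does not define which data are relevant, and it sets no time before which they are withheld. Nothing in the available text reconciles it with the double-blind claim in section 3.

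The symptom comparison is at stake. A participant who hears mid-trial how the analysis is going, or sees stool results that seem to show change or no change, may form a view about true or sham and rate later symptoms accordingly. The design adds to the exposure because true or sham is drawn again at 4 weeks: feedback on the first period could colour ratings in the second. It could also colour the two-week follow-up, which the protocol uses to judge whether any benefit lasts.

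**Working it through.** **Inputs.** First questionnaire on day 0, 7-day spacing and 11 collections (section 6); treatment for 8 weeks, or 56 days (section 6); follow-up for two weeks after treatment, with stool samples on days 0, 28, 56, 63 and 70 (section 6 and the text under Figure 2).

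**1. Reproduce the stated count.** End of follow-up = 56 + 14 = day 70. Number of questionnaires = 70/7 + 1 = 11, on days 0, 7, 14, 21, 28, 35, 42, 49, 56, 63 and 70. This agrees with the protocol's 11.

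**2. Count the ratings exposed.** Access has no start or end date, so every rating after baseline can follow some feedback:

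- Post-baseline questionnaires: 11 − 1 = 10.
- On or before day 56: 8 (days 7 to 56).
- After treatment ends: 2 (days 63 and 70).
- After the day-28 stool sample and the switch of period: 6 (days 35 to 70).

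**3. Count the stool samples that could yield feedback in time.** Four of the five (days 0, 28, 56 and 63) are taken before at least one later questionnaire. The number of questionnaires still to come is 10 after day 0, 6 after day 28, 2 after day 56 and 1 after day 63. Whether a sequencing result would be ready in time is unknown, because no turnaround is given. These are counts of opportunity, not of disclosures.

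**4. Set the rules side by side.**

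| Design element | What it requires or permits |
|---|---|
| Double-blind, same-device sham (section 3) | Participants should not learn, or be led to infer, true or sham |
| Self-rated symptoms to day 70 (sections 6 and 9) | That protection should last until the last rating |
| Access rule (under Figure 2) | Analysis progress and own data on request, with no end date and no stated exclusion |

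The third row can be made consistent with the first two only by adding a restriction that the available text does not contain.

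**5. Size.** An estimate would need the proportion of participants who ask, what they are told, how far it moves later ratings, and whether it moves them alike in true and sham. The documents give none of these. The last matters most: equal shifts in the same direction cancel in the comparison, a shift in one group only biases it, and opposite shifts add. No numerical estimate is therefore offered.

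**The case against.** The strongest reply is that the sentence is narrower than it looks. It closes a two-sentence paragraph whose first sentence is about gut microbiota, so the data meant may be each participant's own microbiota results, and progress may mean no more than study status. The study is called double-blind, so access would ordinarily be understood to operate within the blind. On that reading the route to bias is weak: participants already know the scores they gave, no sequencing turnaround is stated, nothing shows that an individual 16S profile would reveal true or sham, and section 9 describes no interim comparison of groups. Consent pages are not among the documents reviewed and might contain limits.

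Much of this stands. A reader might infer from the sentence that participants can ask for their allocation; no text says so. A reader might also infer that those with worse symptoms would ask more often, or that staff answering requests would see interim results. The documents say nothing about who asks, who answers, or whether interim results exist.

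The reply does not remove the point. The text does not impose the narrow reading, since progress of the analysis goes beyond personal microbiota data. Even on that reading, feedback before day 70 can shape what a participant believes about the stimulation, whether or not the belief is correct. If the narrow meaning was intended, saying so is part of the repair.

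**Conclusion.** The point holds in a limited form. The protocol states an access rule with no visible limit that is in tension with its own double-blind claim, over a period containing all 10 post-baseline self-ratings. This is an avoidable risk of bias in the self-rated symptom outcomes, of a size the documents do not allow anyone to estimate. It should be corrected.

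Two stronger conclusions are not supported. The documents do not show that the blind was or would be broken, because release of allocation is nowhere stated. Nor can this be called bias in the trial's primary outcome: none is named, and section 2 lists symptoms, gut microbiota, and intestinal inflammation with metabolic markers together as objectives. Feedback that changes self-report would not directly alter the stool measurements.

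The conclusion assumes that the access rule applies during follow-up, as its wording says, and that no limit appears in the consent pages, which were not available.

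**What to change.** Amend the sentence to say three things:

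- A participant's own results are released on request after that participant's day-70 questionnaire and sample, except findings needed for safety or care.
- Allocation, device-setting information that reveals allocation, and any between-group results are released only after the last participant's day 70 and data lock.
- Before then, information on progress is confined to the status of the study.

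Align the consent wording if it makes the same offer.

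The cost is one amended protocol statement and, if needed, matching consent text. It narrows something participants are currently offered, so the reason should be explained to them. A participant who asks on day 0 would wait 70 days, or 10 weeks, for personal results. Those enrolled early would wait longer for their allocation; how much longer depends on the length of recruitment, which the available text does not give. The right to one's own data is deferred, not removed, and neither the sample size nor the visit schedule changes.

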#### 7.Description of concha vagus nerve stimulator

- 1、 brand: Ruishan
- 2、Model: tVNS501
- 3、Core technical indicators:
- (1) The stimulation location should be the concha boat, which is enriched in the vagus nerve.
- (2) Built-in rechargeable lithium battery.

(3) It has three output modes: ① Mode 1: randomly transform between pulse amplitude 0 level and set level, pulse width 200 $\mu$ s, pulse frequency in the range of 1-120Hz; ② Mode 2: pulse width 200 $\mu$ s; The pulse frequency is 20Hz for 7s and 4Hz for 3s, alternating between the two. ③ Custom mode programmable: pulse width (100-2000 $\mu$ s), pulse frequency (1-120Hz), pulse on time (10-200s), pulse off time (10-200s).

(4) The duration of stimulation can be set to 0-480min

(5) The stimulation output amplitude can be set to 0-60 levels, and the current can be adjusted to 0-50mA. The current increases linearly with the increase of the output amplitude and can be adjusted freely.

4, output waveform:

| professional
Patterns | Monopulse schematic | Parameters             | Programmable range  |
|--------------------------|---------------------|------------------------|---|
|                          | $\Box$              | Pulse amplitude        | Change randomly between level 0 and set level                                 |
| A mode                   |                     | Pulse width (μs)       | 200, error ±10%   |
|                          |                     | Pulse frequency (Hz)   | Vary randomly in the range 1-120  |
|                          |                     | Pulse width (μs)       | 200, error ±10%   |
| B mode                   |                     | Pulse frequency (Hz)   | 1
20Hz run 7s, 4Hz run 3s, alternating
1
between the two, error 土25% |
|                          |                     |                        | 100,000,  |
|                          |                     | Pulse width (μs)       | 100, 200, error ±10%  |
| Custom                   |                     | Pulse frequency (Hz)   | Range 1-120, error $\pm 10\%$   |
| Modes                    |                     | Pulse on time (s)      | Range 10-200, error ±10%  |
|                          |                     | Pulse closing time (s) | 
Range 10-200, error ±10%
  |

#### 5、Functions

The current approved indications for concha-vagus nerve stimulation are as following: for the adjunctive treatment of sleep disorders, anxiety, loss of appetite, fatigue, and diabetes. In foreign countries, concha vagus nerve stimulation has been approved for the adjuvant treatment of epilepsy and depression. At present, some hospitals in China have introduced new technologies for the treatment of disorders of consciousness, stroke rehabilitation, migraine, epilepsy, pain intervention and so on. At the same time, a number of scientific research papers using the device are published every year, including the journal Brain Stimulation has also included research papers on the device.

6, configuration requirements: no installation, direct use. It is convenient to carry, can be opened at any time to stimulate, and does not affect daily work and life.

7, consumables: no consumables

8. Hospitals currently using the equipment of the same brand and model:

General Hospital of the People's Liberation Army

Sichuan West China Hospital

Beijing Xuanwu Hospital

Beijing Tiantan Hospital

Shanghai Mental Health Center The First Affiliated Hospital of Zhejiang University School of Medicine Jiangsu Provincial People's Hospital Fujian Medical University Union Hospital The First Affiliated Hospital of Sun Yat-sen University Beijing Aviation General Hospital Xijing Hospital of Air Force Medical University The First Affiliated Hospital of Army Medical University Xiangya Boai Rehabilitation Hospital, Hunan Province People of Henan Province Anhui Provincial Hospital

#### 8. Possible risks and preventive measures

#### 1. Possible risks:

① During the study period, if the patient's skin is allergic to the ear electrode, the use of the ear electrode can be immediately suspended, and the stopping date and time can be recorded.

② If the current density of the electrode exceeds 2mA(r.m. s)/cm2, special attention should be paid to the use of the electrode. In case of discomfort, please stop using the electrode immediately or reduce the pulse amplitude.

2. Preventive measures:

If the symptoms of patients are not improved significantly after receiving otovagus nerve stimulation, the researchers of this experiment, as digestive specialists, will give further professional guidance, including drugs, psychological counseling, traditional Chinese medicine and other comprehensive programs, in order to improve the symptoms of patients.

#### 9. Data collection and statistical analysis

The degree of pain, the frequency of diarrhea, and the degree of abdominal distension were used to evaluate the changes in the patient's irritable bowel status. The degree of pain refers to the use of psychometric practices to evaluate the patient's subjective feeling, which is also considered to be the main factor to evaluate the poor health-related quality of life (HRQL). The severity of irritable bowel syndrome was measured according to the Gastrointestinal Symptom Rating Scale for Irritable Bowel Syndrome (GSRS-IBS). On the GSRS-IBS scale, a score of 1 to 3 is defined as mild symptoms, a score of 4 or 5 as more severe, and a score of 6 or 7 as extremely severe.

Two-way analysis of variance (ANOVA) was used for statistical analysis. Two-sided t test was used for pairwise comparison, and p value was corrected for multiple comparisons. Kruskal-Wallis test was used for multiple group comparison. Spearman correlation analysis was used to determine the correlation between gut microbiota alterations and biological and pathological parameters related to constipation, with p values corrected by Benjamini-Hochberg method (Benjamini and Hochberg, 1995). A False Discovery Rate (FDR) threshold of 0.1 was used to consider the p value statistically significant. p < 0.05 or p < 0.01 was considered statistically significant. All rule plots were generated using GraphPad Prism version 8.0 (La Jolla, CA, United States). All statistical analyses were performed using GraphPad prismore and R(version 4.1.2,https://www.r-project.org/)

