#### 5. Estimation of sample size

Forty patients with diarrhea-predominant irritable bowel syndrome

[figure not shown]

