| 9. Have you   |   |   |   |   |   |   |   |
| ever been     |   |   |   |   |   |   |   |
| bothered by   |   |   |   |   |   |   |   |
| J             | 1 | 1 | 1 | 1 | 1 | 1 |   |

| the urgent      |  |  |  |  |
|-----------------|--|--|--|--|
| need to         |  |  |  |  |
| defecate (the   |  |  |  |  |
| need to go to   |  |  |  |  |
| the toilet to   |  |  |  |  |
|                 |  |  |  |  |
| defecate)?      |  |  |  |  |
| 10. Do you      |  |  |  |  |
| have the        |  |  |  |  |
| feeling that    |  |  |  |  |
| your bowel      |  |  |  |  |
| movements       |  |  |  |  |
| are             |  |  |  |  |
| incomplete?     |  |  |  |  |
| 11. Do you      |  |  |  |  |
| feel full       |  |  |  |  |
| soon after      |  |  |  |  |
| you start a     |  |  |  |  |
| meal?           |  |  |  |  |
| 12. Do you      |  |  |  |  |
| still feel full |  |  |  |  |
| long after      |  |  |  |  |
| you stop        |  |  |  |  |
| eating?         |  |  |  |  |
| 13. Do you      |  |  |  |  |
| have            |  |  |  |  |
| significant     |  |  |  |  |
| abdominal       |  |  |  |  |
| swelling?       |  |  |  |  |

| The following questions relate to the         | no | A little | More | Quite a lot | Totally so |
|---|----|----------|------|-------------|------------|
| symptoms of irritable bowel syndrome.         |    | bit      |      |             | 5          |
| The severity or intensity of the following    | 0  | 1        | 2    | 3           | 4          |
| symptoms during the past week                 | 0  | -        | -    |             |            |
| 1. I feel helpless because of my bowel        |    |          |      |             |            |
| movements                                     |    |          |      |             |            |
| 2. The smell caused by my stool makes         |    |          |      |             |            |
| me feel embarrassed                           |    |          |      |             |            |
| 3. I worry about how much time I spend        |    |          |      |             |            |
| in the bathroom                               |    |          |      |             |            |
| 4. Because of my defecation problems, I       |    |          |      |             |            |
| feel vulnerable to other diseases             |    |          |      |             |            |

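### Section 9 names a two-way ANOVA with no factors, patient term or pairing, although each patient gives 11 scores and is re-randomised at week 4; the wording admits both valid and invalid analyses

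*Combined protocol and SAP*

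**What the plan says.** Section 9 of the combined protocol and SAP holds the whole statistical plan. On the model it says "Two-way analysis of variance (ANOVA) was used for statistical analysis". On further tests it says "Two-sided t test was used for pairwise comparison, and p value was corrected for multiple comparisons" and "Kruskal-Wallis test was used for multiple group comparison". It does not say which two factors enter the ANOVA, which visits are used, whether patient is in the model, whether the ANOVA is ordinary or repeated-measures, or whether the t tests are paired. No other section supplies this.

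Section 6 sets the data structure: "Patients completed questionnaires on day 0 and every other 7 days thereafter, for a total of 11 questionnaire collections". It also sets the allocation: "Each patient was randomly selected for true stimulation or sham stimulation every 4 weeks", which gives four sequences (true-true, true-false, false-true, false-false). Section 5 gives the size: "Forty patients with diarrhea-predominant irritable bowel syndrome".

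**The concern.** Scores from one patient are correlated, and half of the four sequences change stimulation midway. An analysis that treats every questionnaire as an independent observation claims far more information than 40 randomised patients provide.

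The error goes in two directions. A comparison of groups or of stimulation averaged over visits is tested against too small a variance and over-rejects. A group-by-visit comparison, where a switch between true and sham would show, is tested against a variance that still contains the differences between patients, so it under-rejects and can miss a real effect. The wording leaves the choice between valid and invalid forms open until after the data are seen.

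**Working it through.** **Inputs from the documents.** 40 patients (section 5). Questionnaires on days 0, 7, ..., 70, which is 11 (section 6), so 40 × 11 = 440 scores if complete. Eight of the 11 fall on days 7–56, so 40 × 8 = 320 scores. Four sequences (section 6). Nominal level 0.05 (section 9).

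**Assumptions.** 10 patients per sequence, complete data, normal scores with SD 1. The within-patient correlation is not given, so a range is used: exchangeable ρ = 0.1–0.7, or AR(1) with lag-1 correlation r = 0.3–0.8. The readable text of section 5 gives no effect size, SD or power, so the plan has no figure to reproduce beyond these counts.

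**Step 1. Ordinary ANOVA, four sequences by 11 visits, sequence main effect.** Error df = 440 − 44 = 396 and the critical F(3, 396) is 2.627. With exchangeable correlation the sequence mean square is inflated by 1 + 10ρ, so rejection under the null is about P[F(3, 36) > 2.627/(1 + 10ρ)].

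**Step 2. Ordinary ANOVA, current true/sham by visit, days 7–56.** Error df = 320 − 16 = 304. Each patient contributes a signed sum of 8 scores. Its variance is 8 + 56ρ for patients who stay on one stimulation and 8 − 8ρ for those who switch. The average is 8 + 24ρ = 8(1 + 3ρ), so the inflation is 1 + 3ρ. For AR(1) it is 1 + (3r + 2r² + r³)/2. Rejection is about 2Φ(−1.96/√inflation).

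| Assumed correlation | Sequence effect: formula | Sequence effect: simulated | Current stimulation: inflation | Current stimulation: formula | Current stimulation: simulated |
|---|---|---|---|---|---|
| Exchangeable 0.1 | 28% | 27% | 1.30 | 9% | 9% |
| Exchangeable 0.3 | 58% | 58% | 1.90 | 16% | 15% |
| Exchangeable 0.5 | 73% | 73% | 2.50 | 22% | 22% |
| Exchangeable 0.7 | 80% | 80% | 3.10 | 27% | 26% |
| AR(1) 0.3 | – | 22% | 1.55 | 12% | 12% |
| AR(1) 0.5 | – | 39% | 2.06 | 17% | 17% |
| AR(1) 0.8 | – | 71% | 3.10 | 27% | 27% |

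The simulations used 8,000 null trials per setting for the sequence effect and 20,000 for current stimulation. Separate runs differ by about a point, hence the ranges of about 21–81% and 9–28%. At zero correlation both tests reject about 5%.

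**Step 3. Group-by-visit test in the same ordinary ANOVA.** With exchangeable correlation its mean square has null expectation 1 − ρ against an error of 1. Simulated null rejection is 1.8% at ρ = 0.1 and about 0% from 0.3 upward; for AR(1) 0.3, 0.5 and 0.8 it is 3.5%, 2.4% and 0.4%. Power for a 0.5 SD effect present only during true stimulation, ordinary against repeated-measures with Greenhouse-Geisser:

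- 3% v 74% at exchangeable 0.5
- 10% v 42% at AR(1) 0.8
- 27% v 34% at AR(1) 0.5
- 34% v 35% at AR(1) 0.3

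The loss is large when correlation is long-range and small when it is short-range.

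**Step 4. Readings that are valid.** A 2×2 ANOVA (period-1 by period-2 stimulation) on one value per patient rejects 4.4–5.4% of null trials. A repeated-measures ANOVA that tests sequence against patients (36 df) rejects 4.7–5.5%. Its group-by-visit test with Greenhouse-Geisser rejects about 3–5%.

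**Step 5. t tests.** An unpaired true v sham t test on 20 v 20 patients at day 28 holds 4.7–5.4%. Pooling days 7–28 as if independent has the same 1 + 3ρ inflation as step 2 and rejects about 9–27%.

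**The case against.** The strongest reply is that this is under-specification and not a wrong analysis. That stands. The documents nowhere say that an ordinary ANOVA will be run on all 440 scores, and the four sequences form a natural 2×2 layout in which a two-way ANOVA on one value per patient fits the sentence literally and is valid.

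A reader might infer from the largest figures that the trial's false-positive rate is 20–80%. The documents do not support that. Those figures belong to one layout, the four-sequence main effect averaged over baseline, both periods and follow-up, which is not the true v sham question. For current stimulation the inflation is about 9–28%. Weaker correlation gives less: even the four-sequence test rejects only 9–14% at AR(1) 0.1–0.2. Nor are all tests inflated, since the group-by-visit test errs the other way.

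It is also fair that section 9 does not tie the t tests or Kruskal-Wallis to the weekly scores, so step 5 applies only if visits are pooled.

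What does not stand is that silence is harmless. Every positive correlation tried in step 2 inflated the ordinary stimulation test, and scores from the same patient a week apart are unlikely to be uncorrelated.

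**Conclusion.** The point holds as a gap in specification that matters. One sentence of the plan admits analyses with a 5% error rate and analyses with about 9–28% (current stimulation, days 7–56) or about 21–81% (four-sequence main effect, all visits). It also admits a group-by-visit test at about 0–4% that can lose much of its power. The inflated rates are conditional on an ordinary ANOVA over all visits, on 10 patients per sequence with complete data, and on the assumed correlations. They are not a property of the plan as written. That the plan lacks factors, a patient term and pairing does not depend on any of these assumptions.

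**What to change.** Replace the ANOVA sentence in section 9 with:

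> For each questionnaire score, one mean per patient per 4-week period (days 7–28 and days 35–56) is analysed in a linear mixed model with a patient random intercept and fixed effects for period, day-0 score, current-period stimulation (true/sham) and previous-period stimulation (0 in period 1; +0.5 after true and −0.5 after sham in period 2). The stimulation effect is tested with t on 36 df or Kenward-Roger. Any t test or Kruskal-Wallis test uses one value per patient, and within-patient comparisons are paired. Days 63 and 70 are compared by sequence group, one value per patient per day.

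In simulation this model rejects 3.5–5.4% of null trials under exchangeable, AR(1) and mixed correlation. It holds 4.4–5.0% when a patient-by-period variance of 0.2–0.3 is added. Its power for a constant 0.5 SD effect without carryover is 83–99%. A mixed model on the weekly scores with a random intercept and AR(1) errors is not recommended as the lead analysis, because that same added variance raises its null rejection to about 10–14% with t on 36 df.

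An acceptable alternative that keeps the sponsor's method is a repeated-measures two-way ANOVA (sequence group by visit) with patient as the matching factor and a Greenhouse-Geisser correction.

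The cost is SAP wording and slightly more analysis work, with no new data. Averaging over a period gives up some power if the effect builds up slowly.

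### Section 9 defines no true-versus-sham test; a day-0-adjusted contrast of the randomised period-1 groups, with one score and one alpha, should be the main analysis

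*Combined protocol and SAP*

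**What the plan says.** Section 3 says patients are "randomly assigned to undergo either real tVNS (transcutaneous vagus nerve stimulation) or sham TVNS" at different times. Section 6 adds that "Each patient was randomly selected for true stimulation or sham stimulation every 4 weeks" over 8 weeks, "resulting in a total of 4 groups, namely, true-true, true-false, false-true, and false-false". The readable text gives no allocation ratio and describes no washout; Figures 1 and 2 cannot be seen.

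Section 6 also says: "Patients completed questionnaires on day 0 and every other 7 days thereafter, for a total of 11 questionnaire collections". Stool is sampled on days that include 0, 28 and 56. The microbiota and metabolite aim is worded as change from before to after use of the device.

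Section 9 says: "The degree of pain, the frequency of diarrhea, and the degree of abdominal distension were used to evaluate the changes" in bowel status. It then gives GSRS-IBS as the severity measure, where "a score of 1 to 3 is defined as mild symptoms". The analysis paragraph opens "Two-way analysis of variance (ANOVA) was used for statistical analysis" and adds two-sided pairwise t tests with an unnamed multiplicity correction, Kruskal-Wallis for several groups, and Spearman correlations with a false discovery rate of 0.1. On significance it says: "p < 0.05 or p < 0.01 was considered statistically significant".

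**The concern.** The randomised question is whether stimulation does better than sham. Section 9 does not define the test that answers it. The two ANOVA factors could be stimulation and time, sequence group and time, or stimulation in period 1 and stimulation in period 2. The t tests could be between any of the six sequence pairs or between pooled groups. Each choice changes the effect being estimated, the number of patients compared and whether the day-0 score is used.

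The outcome is equally open: three symptoms and GSRS-IBS are listed, none is primary, and it is not said whether a GSRS-IBS item, mean or total is analysed. With 11 questionnaires, several outcomes and two thresholds, the contrast, visit, score and alpha could all be settled after the codes are opened, and the reported p value would then lose its stated meaning.

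For microbiota and metabolites, a before/after change within patients mixes the stimulation effect with sham response and the passage of time. The trial has a sham group to remove exactly that.

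**Working it through.** **Plan's own figures.** Section 5 gives 40 patients. Its readable text has no effect size, SD or power, and a figure there is not shown, so 40 cannot be reproduced and no missing calculation is claimed. The questionnaire count does reproduce with weekly forms: 70/7 + 1 = 11 (a 14-day interval would give 6). Days 0 and 28 are therefore scheduled.

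**Assumptions.** Equal allocation, so 20 true v 20 sham in period 1 and 10 per sequence; two-sided 0.05; 80% power; correlation r between any two visits of 0.3/0.5/0.7, equal for all pairs. Variances are in units of the score's variance. The detectable difference is a noncentral-t multiplier times the standard error: 2.877 (37 df), 2.8749 (38 df), 2.963 (18 df).

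**Single-visit readings, r = 0.3/0.5/0.7**

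| Test | Variance | Value | Detectable (SD) |
|---|---|---|---|
| Day-28 ANCOVA on day 0 | (2/20)(1 − r²)(37/36) | 0.0935/0.0771/0.0524 | 0.88/0.80/0.66 |
| Day-28 score, unadjusted | 2/20 | 0.10 | 0.91 |
| Day 0-to-28 change (stimulation by time) | (2/20) × 2(1 − r) | 0.14/0.10/0.06 | 1.08/0.91/0.70 |
| One sequence pair, 10 v 10, uncorrected | 2/10 | 0.20 | 1.32 |

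The factor 37/36 allows for chance day-0 imbalance. The ANCOVA variances were checked by 20,000 simulated trials at each r: 0.095/0.076/0.052.

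Power for 0.8 SD is 72/80/93% with ANCOVA, 69% unadjusted, 55/69/89% with change and 40% for one pair. Against the better of the unadjusted and change tests, ANCOVA gains 0.03/0.11/0.05 SD; that test would need about 43/52/46 patients to match ANCOVA with 40. ANCOVA beats the unadjusted score for r above 0.16 and the change for r below 0.95.

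**Readings that use several weekly forms** (effect constant over the visits averaged). The mean of k visits has variance (1 + (k − 1)r)/k.

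- Days 7 to 28 (k = 4) minus day 0: 0.10[(1 + 3r)/4 + 1 − 2r] = 0.0875/0.0625/0.0375, detecting 0.85/0.72/0.56 SD. This is more precise than day-28 ANCOVA.
- Days 14 to 28 (k = 3) minus day 0: 0.10[(1 + 2r)/3 + 1 − 2r] = 0.0933/0.0667/0.0400, detecting 0.88/0.74/0.57 SD.
- The same days 14 to 28 mean by ANCOVA: 0.10[(1 + 2r)/3 − r²](37/36) = 0.0456/0.0428/0.0319, detecting 0.61/0.60/0.51 SD.

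Like for like, then, using day 0 as a covariate improves on subtracting it.

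**Both periods.** A model of days 28 and 56 given day 0, with a common effect and additive carry-over, has standard error 0.210/0.188/0.152; times 2.80 this is 0.59/0.53/0.43 SD. Baseline-adjusted true-true v false-false at day 56, about 10 v 10 (35 df, variance 0.20(1 − r²)), detects 1.23/1.12/0.92 SD. These two rows omit the small allowance for chance day-0 imbalance.

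**The case against.** The strongest reply is that an undefined ANOVA has no fixed precision. With weekly forms, a natural reading is stimulation by time over all period-1 visits, which matches or beats day-28 ANCOVA in the same randomised groups and needs no carry-over assumption. That stands. A reader might infer that day-28 ANCOVA is the most precise analysis available, or that any two-way ANOVA would be inferior here; the calculations do not support either. What remains is that the weekly reading assumes a constant effect, that its day-7 form reaches back before treatment under Table 1's 2-week recall, and that it too gains from day-0 adjustment.

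The two-period model is also more precise if carry-over is additive. Section 6 treats persistence after stopping as an open question, so ranking that model second is a judgement. So is putting a 4-week contrast first when Section 1 states an 8-week aim.

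The score is open to argument as well. Section 9 gives pain special weight for quality of life, and the 13 GSRS-IBS items include constipation and dry stools in a diarrhoea-predominant population. The choice belongs to the sponsor.

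The two p thresholds may be only figure-annotation levels. Even so, the main test needs one alpha.

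Finally, that day-28 GSRS-IBS exists is an inference: Section 6 says the questionnaires are in Table 2, while GSRS-IBS is Table 1.

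**Conclusion.** The point holds as a should-fix. Section 9 does not define the randomised comparison, its visit, its use of day 0, its score or its alpha, and the before/after wording for microbiota and metabolites cannot isolate the stimulation effect. Adjusting a true-versus-sham contrast for day 0 is a definite improvement at no cost in patients.

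The gain is modest against the better single-visit 20 v 20 test and larger against comparisons of single sequences (0.88/0.80/0.66 v 1.32 SD). These sizes rest on assumed correlations, equal allocation and 40 analysed patients. A 16 v 24 split would raise the ANCOVA figures by less than 0.02 SD.

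The case for day 28 is a clean contrast: it precedes any switch, and its recall window (days 14 to 28) lies inside period 1. It is not a case for maximum precision. A reader might also infer that the test was, or will be, picked to suit the results. The documents show only that nothing prevents this.

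**What to change.** Before unblinding, state in Section 9:

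1. **Main test.** (true-true + true-false) v (false-true + false-false) in period 1, by ANCOVA with the day-0 score as covariate. Day-28 GSRS-IBS is the default; the mean of days 14 to 28 is an acceptable alternative.
2. **One score.** GSRS-IBS mean or pain, at the sponsor's choice, with the remaining symptoms secondary. The 1-to-7 severity bands fit an item or a mean, not a 13-item total.
3. **One alpha.** Two-sided 0.05.
4. **Support for the 8-week aim.** A two-period mixed model of days 28 and 56 (day-0 score, period, current and previous stimulation, random patient) with its carry-over assumption stated, and a baseline-adjusted true-true v false-false contrast at day 56.
5. **Microbiota and metabolites.** The same randomised contrast, using the day-0 and day-28 stool samples, in place of before/after change alone.

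The sponsor should confirm that GSRS-IBS is given on days 0 and 28 and correct the table reference in Section 6. If so, the cost is wording only: no extra patients, visits or samples. The drawback is that the main test estimates a 4-week effect and leaves period 2 out, while the 8-week contrast stays at about 10 v 10.
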